APPENDIX IV: ENROLLMENT AND REGISTRATION PROCESS

APPENDIX V: VESSEL TREATMENT & RANDOMIZATION

[REDACTED]

[REDACTED]

[Redacted text block]

[Redacted text block]

[REDACTED]

APPENDIX VI: RISK STRATIFICATION OF CARDIAC CATHERIZATION, STENTING AND PERCUTANEOUS TRANSCATHETER CORONARY ANGIOPLASTY

Potential risks associated with the study device and everolimus were described in the original protocol. Based on additional clinical and commercial experience, and more conservative grouping of MedDRA Preferred Terms, Abbott Vascular can now provide a consolidated list of anticipated adverse events and, in alignment with ISO14155:2011 requirements, the estimated frequencies of those risks.

There is extensive clinical and commercial experience worldwide with cardiac catheterization and interventional procedures. It is expected that the risks will not be significantly different with the use of the Absorb BVS and XIENCE V stent in this trial. The incidence rates of the known complications that may arise from a stenting procedure were obtained from the pooled XIENCE V trials conducted by AV (Spirit First, Spirit II, Spirit III RCT, Spirit III JPN, Spirit III 4.0 mm, Spirit IV, Spirit V Diabetic, Spirit V Registry, Spirit Women, XV USA, XV DAPT, and XV India using MedDRA Preferred Terms of site-reported 1 year adverse events regardless of relationship to device or procedure) and were classified using the frequency categories as below. Death and stent thrombosis within 1 year have been observed in < 2.0% of the patients enrolled in these trials.

1. Very common: $\geq 10\%$: Unstable or stable angina pectoris
2. Common: $\geq 1.0\%$ to $< 10\%$: Cardiac, pulmonary or renal failure; access site complications including pain, hematoma, or hemorrhage; vascular complication including at the entry site, which may require vessel repair; coronary artery dissection; arrhythmia including atrial and ventricular; myocardial infarction, including acute myocardial infarction; nausea and vomiting; hypotension; hypertension; restenosis
3. Uncommon: $\geq 0.1\%$ to $< 1.0\%$: Cardiac arrest; emergent or non-emergent surgery; allergic or hypersensitivity reactions to contrast agent or platinum, polymer poly (L-lactide) (PLLA), polymer poly (D,L-lactide) (PDLLA), and drug reactions to everolimus, antiplatelet drugs or contrast agent; bleeding complications which may require transfusion; coronary artery spasm; distal emboli; fever; catheter site infection or pain; myocardial ischemia; palpitations; coronary artery perforation; pericarditis; peripheral ischemia (due to vascular injury); pseudoaneurysm; pulmonary edema; stroke/CVA/TIA; total occlusion of coronary artery; ventricular tachycardia; and ventricular fibrillation; vessel dissection
4. Rare: $\geq 0.01\%$ to $< 0.1\%$: Arteriovenous fistula; cardiac tamponade; coronary artery embolism; arterial injury; procedural nausea; shock; peripheral artery dissection; peripheral nerve injury; renal insufficiency; pericardial effusion
5. Very Rare: $< 0.01\%$ (including not reported AEs): Abrupt coronary artery closure; coronary artery aneurysm; arterial rupture; everolimus IFU risks.

Some IFU risks, including everolimus risks have not been observed in AV clinical studies. These risks are listed in the very rare category. There may be risks related to the device that are unknown at present. Likewise the exact frequency of the risk might be unknown.

1. SYNOPSIS OF STUDY DESIGN AND PROCEDURES

1.1 Purpose of the Statistical Analysis Plan

This statistical analysis plan (SAP) is intended to provide a detailed and comprehensive description of the planned methodology and analysis to be used in the ABSORB IV RANDOMIZED CONTROLLED TRIAL, the second part of Protocol 10-392. This plan is based on the [REDACTED], March 16, 2017 of the study protocol.

1.2 Study Objectives

- **ABSORB IV Primary Objectives:**

- To evaluate 30-day clinical outcomes of the Absorb BVS[&] compared to XIENCE* in the treatment of subjects with ischemic heart disease caused by up to three *de novo* native coronary artery lesions in a maximum of two epicardial vessels, with a maximum of two lesions per epicardial vessel..
- To evaluate long-term clinical outcomes of Absorb BVS compared to XIENCE in the treatment of subjects with ischemic heart disease caused by up to three *de novo* native coronary artery lesions in a maximum of two epicardial vessels, with a maximum of two lesions per epicardial vessel.

- **ABSORB IV Secondary Objective:**

- To evaluate 1-year clinical outcomes of the Absorb BVS[&] compared to XIENCE* in the treatment of subjects with ischemic heart disease caused by up to three *de novo* native coronary artery lesions in a maximum of two epicardial vessels, with a maximum of two lesions per epicardial vessel..
- To evaluate the incidence of angina occurring within 1-year, with treatment of Absorb BVS compared to XIENCE.

1.3 Study Design

ABSORB IV is a prospective, randomized (1:1, Absorb BVS to XIENCE), single-blind, multi-center study, registering approximately 2600 subjects at approximately 140 sites.

The enrollment of the 2600 subjects in ABSORB IV will start after the enrollment completion of the 2000 primary analysis subjects in ABSORB III.

Table 1 provides the device sizes, the reference vessel diameter (RVD) and lesion length for ABSORB IV.

[&] The term “Absorb BVS” will be used to represent both Absorb[™] BVS and Absorb GT1[™] BVS.

^{*} Commercially approved XIENCE family stent system, inclusive of XIENCE V, XIENCE PRIME, XIENCE Xpedition, XIENCE Alpine, XIENCE Pro (OUS only), and XIENCE Pro^X (OUS only).

Table 1. Absorb BVS and XIENCE Sizes

| Device | Lesion and Device Sizes | |
|--|--|--|
| | RVD ¹ | Lesion Length ¹ |
| Absorb BVS ⁴ (Target lesion) | RVD ≥ 2.50 mm - ≤ 3.75 mm Scaffold diameter: 2.5, 3.0 and 3.5 mm | Lesion length ≤ 24 mm Scaffold Length ² : 8, 12, 18 and 28 mm ³ |
| XIENCE ⁵ (Target lesion) | RVD ≥ 2.50 mm - ≤ 3.75 mm Stent diameter: 2.5, 2.75, 3.0, 3.25, 3.5, 4.0 mm | Lesion length ≤ 24 mm Stent Length: 8, 12, 15, 18, 23 and 28 mm ³ |

¹ Reference vessel diameter (RVD) and lesion length are based on visual estimation.

² Both the 8 mm and 12 mm lengths will be available for the 2.5/3.0 diameter Absorb BVS. Only the 12 mm length will be available for the 3.5 mm diameter. The commercially approved CE marked 23mm Absorb BVS device will not be used in this study.

³ For target lesion, planned overlapping is not allowed (i.e. the lesion must be eligible for treatment with a single stent). However, bailout overlapping is allowed if required.

⁴ Once Absorb GT1™ BVS System is commercially available, it can also be used in the ABSORB IV trial.

⁵ XIENCE V, XIENCE Prime, XIENCE Xpedition, XIENCE Alpine, XIENCE Pro, and XIENCE Pro^X will be used in this study.

All registered subjects in ABSORB IV will receive the following clinical follow-up:

- 30 ± 7 days follow-up telephone contact/office visit
- 90 ± 14 days follow-up telephone contact/office visit
- 180 ± 28 days follow-up telephone contact/office visit
- 270 ± 28 days follow-up telephone contact/office visit
- Annual visits: 1-7 years ± 28 days follow-up telephone contact/office visit

All registered subjects in ABSORB IV will potentially be followed up at 8 (± 28 days) and/or 9 and/or 10 years (± 28 days) via telephone contact/office visit if it is necessary as determined by the Sponsor. Patients will be consented for these additional follow-up visits at the time of written informed consent.

1.3.1 Primary Endpoints

The primary endpoints of the ABSORB IV trial are:

1. TLF through 30 days: the percentage of patients who experienced TLF within 30 days, tested for non-inferiority of Absorb BVS to XIENCE.

This analysis will consist of ~2600 subjects in ABSORB IV.

1.3.2 Secondary Endpoint

1.3.2.1 Powered Secondary Endpoint #1: TLF through 1 year

TLF through 1 year: the percentage of patients who experienced TLF within 1 year, tested for non-inferiority of Absorb BVS to XIENCE.

[figure not shown]
This analysis will consist of ~2600 subjects in ABSORB IV.

1.3.2.2 Powered Secondary Endpoint #2: Angina through 1 year

Angina through 1 year will be tested first for non-inferiority of Absorb BVS to XIENCE with reflex testing to superiority.

This analysis will consist of ~2600 subjects in ABSORB IV.

- Angina is defined as any angina or angina equivalent symptoms determined by the physician and/or research coordinator after interview of the patient, and as adjudicated by a clinical events committee (CEC).
- This analysis will exclude angina or angina equivalent symptoms that occurred following the index procedure through hospital discharge or 7 days, whichever occurs first.

1.3.2.3 Additional Secondary Endpoints

In ABSORB IV the following clinical secondary endpoints will be analyzed.

- **Acute Success:** (Combined Clinical/Angiographic Endpoint)

- Device success (Lesion level analysis)
- Procedural success (Subject level analysis)
- **Clinical Endpoint** in hospital and at each follow-up point (30, 90, 180, 270 days; 1, 2, 3, 4, 5, 6, 7 years, and potentially 8 and/or 9 and/or 10 years)
 - **Component**
 - Death (Cardiac, Vascular, Non-cardiovascular)
 - Myocardial Infarction
 - Attributable to target vessel (TV-MI)
 - Not attributable to target vessel (NTV-MI)
 - Target Lesion Revascularization (TLR)
 - Ischemia driven TLR (ID-TLR)
 - Non ID TLR (NID-TLR)
 - Target Vessel Revascularization (TVR)
 - ID TVR
 - NID TVR
 - All coronary revascularization
 - **Composite Endpoints**
 - Death/All MI
 - Cardiac Death/All MI
 - Cardiac Death/TV-MI/ID-TLR (TLF)
 - Cardiac Death/All MI/ID-TLR (MACE)
 - Cardiac Death/All MI/ID-TLR/ID-TVR, non TL (Target Vessel Failure, TVF)
 - Death/All MI/All revascularization
 - **Composite Endpoints Scaffold-Thrombosis / Stent Thrombosis (per ARC definition)**
 - Timing (acute, sub-acute, late and very late)
 - Evidence (Definite, Probable)
 - **Rehospitalization**
 - Coronary artery disease related
 - Cardiovascular, non-CAD related
 - Non-cardiovascular related
 - **Repeat coronary arteriography**

[REDACTED]

[REDACTED]

[REDACTED]

[REDACTED]

[REDACTED]

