REFERENCE VESSEL DIAMETER [RVD]

Average diameter of proximal and distal healthy segments by QCA. 10 mm “normal” reference segments are selected proximal and distal to the stenosis and averaged to define the reference vessel diameter (User defined method). A computer-defined interpolated normal segment will be used to calculate percent diameter stenosis.

RESTENOSIS

Re-narrowing of the artery following the removal or reduction of a previous narrowing.

TIMI (THROMBOSIS IN MYOCARDIAL INFARCTION) FLOW GRADES

0. No contrast flow through the stenosis.
1. A small amount of contrast flows through the stenosis but fails to fully opacify the artery beyond.
2. Contrast material flows through the stenosis to opacify the terminal artery segment. However, contrast enters the terminal segment perceptibly more slowly than more proximal segments. Alternatively, contrast material clears from a segment distal to a stenosis noticeably more slowly than from a comparable segment not preceded by a significant stenosis.
3. Anterograde flow into the terminal coronary artery segment through a stenosis is as prompt as anterograde flow into a comparable segment proximal to the stenosis. Contrast

material clears as rapidly from the distal segment as from an uninvolved, more proximal segment.

ACUTE SUCCESS DEFINITIONS

Clinical Device Success (Lesion Basis)

Successful delivery and deployment of the study scaffold/stent at the intended target lesion and successful withdrawal of the delivery system with attainment of final in-scaffold/stent residual stenosis of less than 30% by QCA (by visual estimation if QCA unavailable). When bailout scaffold/stent is used, the success or failure of the bailout scaffold/stent delivery and deployment is not one of the criteria for device success.

Clinical Procedure Success (Patient Basis)

Achievement of final in-scaffold/stent residual stenosis of less than 30% by QCA (by visual estimation if QCA unavailable) with successful delivery and deployment of at least one study scaffold/stent at the intended target lesion and successful withdrawal of the delivery system for all target lesions without the occurrence of cardiac death, target vessel MI or repeat TLR during the hospital stay (maximum of 7 days). In dual target lesion setting both lesions must meet clinical procedure success criteria to have a patient level procedure success.

	Successful Deployment	No Device Deficiencies	QCA requirement	In-hospital AE

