- Please refer to the physician training deck for user guidance in handling procedural issues (e.g., difficulty in re-crossing an implanted scaffold for purposes such as intravascular imaging or post-dilatation if needed).
- Unplanned Lesions
 - In cases where treatment of a target lesion reveals unexpected additional lesion(s), the investigator may treat the lesion(s). This is considered an unplanned lesion.
 - If the lesion meets enrollment criteria both before and after pre-dilatation, the lesion must be treated with the assigned device. This lesion will be considered to be an unplanned target lesion.
 - If the lesion does not meet the enrollment criteria (either before or after pre-dilatation), the lesion must be treated with XIENCE. This lesion will be considered to be an unplanned non-target lesion.
 - Planned treatment of more than two lesions per epicardial vessel or planned treatment of more than three lesions per subject is not allowed.

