2.1.1 Statistics for Continuous Variables

For continuous variables (e.g., age, percent diameter stenosis, and lesion length), results within treatment arm will be summarized with the numbers of observations, means, and standard deviations, and in addition, with medians, quartiles, minimums, maximums, and 95% confidence intervals for the means, when specified. Differences between the treatment arms, when specified, will be summarized with the differences of the two means and 95% confidence intervals for the difference between the means, and p-values from t-test may also be presented for hypothesis generating purposes.

Formulas for calculation of the confidence intervals for the continuous variables are given below:

1. 100(1- α)% Confidence Interval For A Single Mean²

$$\bar{x} \pm t_{\frac{\alpha}{2}} \frac{s}{\sqrt{n}}$$

where:

\bar{x} = sample mean

s = sample standard deviation

n = sample size

$t_{\frac{\alpha}{2}}$ = the alpha/2 t - statistic for n – 1 degrees of freedom

2. 100(1- α)% Confidence Interval For The Difference of Two Means Under The Assumption Of Equal Variances Between The Two Groups²

$$(\bar{x}_1 - \bar{x}_2) \pm t_{\frac{\alpha}{2}} \sqrt{s_p^2 \left(\frac{1}{n_1} + \frac{1}{n_2} \right)}$$

where:

\bar{x}_1 = sample mean for group 1

\bar{x}_2 = sample mean for group 2

$$s_p^2 = \frac{(n_1 - 1)s_1^2 + (n_2 - 1)s_2^2}{n_1 + n_2 - 2}$$

s_1 = sample standard deviation for group 1

s_2 = sample standard deviation for group 2

n_1 = sample size for group 1

n_2 = sample size for group 2

$t_{\frac{\alpha}{2}}$ = the alpha/2 t - statistic for $n_1 + n_2 - 2$ degrees of freedom

3. 100(1- α) % Confidence Interval for the Difference of Two Means under the Assumption of Unequal Variances between the Two Groups²

$$(\bar{x}_1 - \bar{x}_2) \pm t_{\frac{\alpha}{2}} SED$$

With the degrees of freedom for the approximate t statistic is determined by Satterthwaite's formula² as follows:

$$df = \frac{(w_1 + w_2)^2}{\frac{w_1^2}{n_1 - 1} + \frac{w_2^2}{n_2 - 1}}$$

where:

\bar{x}_1 = sample mean for group 1

\bar{x}_2 = sample mean for group 2

s_1 = sample standard deviation for group 1

s_2 = sample standard deviation for group 2

n_1 = sample size for group 1

n_2 = sample size for group 2

$$SED = \sqrt{\frac{s_1^2}{n_1} + \frac{s_2^2}{n_2}}$$

$$w_1 = \frac{s_1^2}{n_1}$$

$$w_2 = \frac{s_2^2}{n_2}$$

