2.1.2 Statistics for Categorical Variables

For categorical variables such as gender, MACE, and TVF, results within treatment arm will be summarized with subject counts and percentages/rates, and where specified in the table mockups, with exact 95% Clopper-Pearson³ confidence intervals. Differences between the two treatment arms, when specified, will be summarized with the difference in percents and the Newcombe⁴ score 95% confidence interval for the difference of two percentages.

For efficacy and safety endpoint(s), relative risks (i.e., the ratio of rates), confidence interval for the relative risks, the difference in rates and the confidence interval for difference in rates (using previously-described formulas), and p-values may also be presented for hypothesis generating purposes. The p-values will be based on either Pearson's Chi-square test or Fisher's exact test by checking the expected frequency for each cell in the 2x2 contingency table against Cochran's rule⁶, i.e., if the expected frequencies for all cells are ≥ 5 , then Pearson's Chi-square test will be used, otherwise Fisher's exact test will be used.

For the determination of event rates at all time points (in-hospital, 30 days, 180 days and 1 to 7 (8/9/10) years), the denominators are defined as below based on the type of events.

- Death/MI/Revascularization (DMR) event

Subjects will be included in the analysis if they either had the DMR event by that time or they did not have the DMR event but had follow-up through that time point. In other words, subjects will be included in a given analysis if it can be determined whether or not the subject would have had the DMR event by the time point.

- Stent/Scaffold Thrombosis, Vascular/Bleeding, CVA, and Angina

Subjects will be included in the analysis if they either had the specific event (for example, for analysis on ST, only ST is considered) by that time or they did not have the event but had follow-up through that time point. In other words, subjects will be included in a given analysis if it can be determined whether or not the subject would have had the event by the time point.

Formulas for calculating confidence intervals for the categorical variables are given below.

1. 100(1- α) % Exact Clopper-Pearson Confidence Interval for A Single Proportion³

$$\text{Lower Confidence Limit} = \frac{x}{x + (n - x + 1)F_{1-\frac{\alpha}{2}}(2(n - x + 1), 2x)}$$

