2.2.3 Other Subgroups

The following subgroups will be evaluated for the ITT population. The treatment comparisons in these analyses are not powered for hypothesis testing and are not meant for confirmatory inference. Baseline demographics, baseline subject characteristics, procedure information, morphology, quantitative coronary angiography, and hierarchical/non-hierarchical adverse event data will be summarized with descriptive statistics. Comparisons will be made between treatment arms within each of these subgroups.

Ethnicity:

- Non-white
- White

Age:

- Age \geq Median, Age $<$ Median
- Age <45 , ≥ 45 and <55 , ≥ 55 and <65 , ≥ 65 and <80 , and ≥ 80

Number of Target Lesion/Vessel Treated:

- Single target lesion/vessel treated, which includes subjects who had only one target lesion/vessel treated
- Dual target lesion/vessel treated, which includes subjects who had two target lesion/vessel treated
- Three target lesion/vessel treated, which includes subjects who had three target lesion/vessel treated.

Angina Status

- Acute coronary syndrome (unstable angina, NSTEMI, recent STEMI)

- Stable angina or silent ischemia
- Recent STEMI
- NSTEMI
- Unstable Angina
- Stable Angina
- Silent ischemia

Antiplatelet Therapy

- P2Y12 Receptor Inhibitor (Yes/No)
- Clopidogrel or Ticlopidine (Yes/No)
- Prasugrel or Ticagrelor (Yes/No)
- Clopidogrel (Yes/No)
- Ticlopidine (Yes/No)
- Prasugrel (Yes/No)Ticagrelor (Yes/No)

RVD by QCA

- $RVD \geq \text{Median}$, $RVD < \text{Median}$
- Small Vessel ($RVD \geq 2.25 \text{ mm}$, $RVD < 2.25 \text{ mm}$)

Implanted Device Diameter

- Device Diameter 2.5 mm vs. 3.0 mm vs. 3.5 mm

Population

- ABSORB III-like (Yes/No)
- ACS (Yes/No)

Implantation technique

- Compete PSP vs Incomplete PSP
 - The implantation technique used during the index procedure must satisfy all of the following criteria to be considered as complete PSP, otherwise it will be incomplete PSP
 1. Pre-dilatation performed
 2. QCA $RVD \geq 2.25 \text{ mm}$
 3. Post-dilatation performed with pressure $> 16 \text{ atm}$ and nominal scaffold diameter $<$ diameter of post-dilatation balloon \leq nominal scaffold diameter + 0.5 mm
- Each of the three individual component of complete PSP listed above (Yes/No)

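### The visible SAP formulas assume independent observations and do not define n for lesion-level device success and QCA variables

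*SAP*

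**What the plan says.** SAP 1.3.2.3 sets two acute-success endpoints side by side with different units: "Device success (Lesion level analysis" and "Procedural success (Subject level analysis". The ABSORB III Appendix II, which ABSORB IV adopts for definitions it does not update, has the matching entry "Clinical Device Success (Lesion Basis".

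Several lesions per subject are expected. In the ABSORB IV Protocol Summary (Treatment Strategy), "planned treatment of more than three lesions per subject is not allowed". That cap covers planned lesions only. A lesion found during the procedure that meets the entry criteria gets the assigned device, and "This lesion will be considered to be an unplanned target lesion". SAP 2.2.3 defines subgroups by number of target lesions, including "Three target lesion/vessel treated, which includes subjects who had three target lesion/vessel treated".

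SAP 2.1.1 opens "For continuous variables (e.g., age, percent diameter stenosis, and lesion length" and then gives t-based intervals for one mean and for a difference of means. SAP 2.1.2 gives the "Exact Clopper-Pearson Confidence Interval for A Single Proportion" and the Newcombe score interval for a difference. In the formulas n is simply the sample size. Both sections make intervals conditional on being specified, partly in table mockups that are not shown. For continuous variables, ABSORB IV protocol section 10.4 states without that condition that 95% intervals for the mean will be calculated.

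**The concern.** Two of the three continuous examples in SAP 2.1.1, percent diameter stenosis and lesion length, are properties of a lesion. So is device success. Lesions in one subject share the patient's disease and usually the procedure, so their outcomes may be positively correlated. A formula that divides by the number of lesions then counts more information than the data hold. Intervals come out too short and p-values too small.

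Clustering does not cancel in the treatment comparison. Randomisation is by subject, so under intent-to-treat all of a subject's lesions fall in one arm and the variance of the difference is inflated too.

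At stake is the stated precision of device success and QCA summaries. SAP 2.2 says its subgroup analyses, which summarise QCA data, are meant for the product's instructions for use.

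**Working it through.** **No figure to reproduce.** The documents give no lesion count, within-subject correlation, device-success rate or interval width for lesion-level results. The effective sample sizes in SAP 1.5 (2574 and 2470) count subjects.

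**Inputs.**
- From the documents: about 2600 subjects randomised 1:1 (SAP 1.3), so about 1300 per arm; at most three planned lesions per subject.
- Assumed: the lesion mix, an intraclass correlation (ICC) of 0.1 to 0.5, and device success of 95% (99% in the comparison arm). Unplanned target lesions are ignored.

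**Step 1: design effect.** With m lesions per subject, DE = 1 + (Σm²/Σm − 1) × ICC, and the correct width is √DE times the unadjusted width. For a 60/30/10% mix of one, two and three lesions:
- Σm per subject = 0.60 + 0.60 + 0.30 = 1.50
- Σm² per subject = 0.60 + 1.20 + 0.90 = 2.70
- 2.70/1.50 = 1.80, so DE = 1 + 0.80 × ICC
- at ICC 0.5, DE = 1.40 and √DE = 1.18; the unadjusted interval is 1 − 1/√1.40 = 15% too narrow.

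| Subjects with 1/2/3 lesions | Lesions per subject | DE, ICC 0.1–0.5 | Correct ÷ unadjusted width | Unadjusted too narrow by |
|---|---|---|---|---|
| 90/9/1% | 1.11 | 1.02–1.11 | 1.01–1.05 | 1–5% |
| 75/20/5% | 1.30 | 1.05–1.27 | 1.03–1.13 | 3–11% |
| 60/30/10% | 1.50 | 1.08–1.40 | 1.04–1.18 | 4–15% |

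**Step 2: size in percentage points.** Take an 80/17/3% mix: 1300 × 1.23 = 1599 lesions per arm. The SAP's intervals (Clopper-Pearson in its standard form) were computed with n and with n/DE.

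| | Clopper-Pearson, 95% success | Width | Newcombe width, 95% vs 99% |
|---|---|---|---|
| Unadjusted | 93.82–96.02% | 2.20 | 2.39 |
| ICC 0.3 (DE 1.127) | 93.73–96.07% | 2.34 | 2.54 |
| ICC 0.5 (DE 1.211) | 93.68–96.11% | 2.43 | 2.64 |

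The width changes by about a quarter of a percentage point at most.

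**Step 3: coverage.** The normal approximation, 2Φ(1.96/√DE) − 1, gives 94.8% at DE 1.02 and 90.2% at DE 1.40. Clopper-Pearson is conservative, so it loses less. Simulated coverage (4000 runs, 1300 subjects, 95% success; Monte Carlo error about 0.4 points) was:

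| Mix | ICC 0.1 | ICC 0.3 | ICC 0.5 | Normal approximation, ICC 0.5 |
|---|---|---|---|---|
| 90/9/1% | 95.0% | 95.8% | 94.5% | 93.7% |
| 80/17/3% | 95.2% | 94.1% | 92.8% | 92.5% |
| 70/25/5% | 95.7% | 93.6% | 92.3% | 91.5% |

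Coverage of about 90–92% appears only at the far corner, with 40% multi-lesion subjects and ICC 0.5. At ICC 0 there is no error.

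**The case against.** The strongest reply is that the visible text does not establish the error.

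- **Redaction.** SAP 2.1.4 is blacked out in full. So are the end of 1.3.2.3, part of 2.1.3, and the text between 2.3 and 2.11. A rule for lesion-level data could be there. A reader might infer that the SAP has no clustering rule; the documents cannot support that. It can be said that 2.1.1 and 2.1.2, which name the variables and give the formulas, show no redaction and make no exception for lesions.
- **Whether intervals are reported, and on what n.** The SAP makes them conditional. SAP 2.1.2 speaks of subject counts and gives gender, MACE and TVF as examples, not device success. So a flat statement that the intervals are too narrow goes too far. The condition carries less weight for continuous variables, given protocol 10.4.
- **QCA.** The visible ABSORB IV endpoint list contains no QCA endpoint. QCA data appear as descriptive summaries, with comparisons between arms within subgroups.
- **Source of correlation.** A reader might assume that all lesions in a subject share one operator and one device. No visible text says one operator treats every lesion. A staged procedure is allowed, and the Protocol Summary has XIENCE used in a lesion where Absorb failed while the remaining lesions receive Absorb. Positive correlation is plausible on patient grounds, but its size is unknown.

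All four points stand as limits on the claim. None removes the gap: the unit of n is undefined and the only visible formulas assume independence.

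**Conclusion.** The point holds in conditional form and is minor. If n counts lesions and within-subject correlation is positive, reported intervals and between-arm p-values for device success and QCA variables will be somewhat too optimistic. With 10–40% multi-lesion subjects and ICC 0.1–0.5, all assumed, correct intervals are about 1–18% wider. Clopper-Pearson coverage generally falls less than the normal approximation suggests.

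A reader might infer that the trial's main conclusions are affected. They are not. TLF is a per-subject count (ABSORB IV protocol 10.1), angina is a percentage of patients (5.2), and the remaining secondary endpoints are descriptive (10.4.3), with SAP p-values labelled hypothesis-generating.

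**What to change.** In SAP 2.1.1 and 2.1.2, state whether n counts lesions or subjects for each lesion-level variable. Where it counts lesions, use an interval clustered on subject: a subject-level bootstrap, or GEE with a robust variance clustered on subject. For device success near 100%, choose a link or interval that stays within 0–1; an identity-link Wald interval may fail to converge or exceed 100%. Keep the present formulas for subject-level endpoints. If a redacted section already handles clustering, a cross-reference from 2.1.1 and 2.1.2 is enough.

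The cost is a few lines of SAP text and standard SAS code, with no change to data collection, sample size or conduct. The price is slightly wider intervals and the loss of an exact interval for device success.
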